14.2. STUDY DRUG COMPLIANCE

The following summaries of study drug compliance will be presented for Cycle 1 and all subsequent cycles, separately:

- Percentage tazemetostat taken (summarized as a continuous variable).

Study Part 1:

Cycle 1: Percentage of tazemetostat taken = $100\% \times \text{Average dose intensity (mg BID/day)} / \text{Planned average dose intensity (mg BID/day)}$.

Cycle 2+: Percentage of tazemetostat taken = $100\% \times \text{Average dose intensity (mg BID/day)} / 800 \text{ mg BID/day}$.

Study Part 2:

Cycle 1: Percentage of tazemetostat taken = $100\% \times \text{Average dose intensity (mg BID/day)} / \text{Planned average dose intensity (mg BID/day)}$.

Cycle 2+: Percentage of tazemetostat taken = $100\% \times \text{Average dose intensity (mg BID/day)} / 800 \text{ mg BID/day}$.

- Category of percentage of tazemetostat taken (using categories $\geq 90\%$, 80% to $< 90\%$, 70% to

< 80%, and < 70%).

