7.5.2. Dose Modification due to Treatment-Related Toxicity

In Cycle 2 and beyond for tazemetostat, other toxicities that, in the opinion of the Investigator are possibly, probably, or definitely related to study treatment, should be managed per [Table 2](#). Toxicities that are felt by the Investigator to be unrelated to tazemetostat but clinically significant should be discussed with the Medical Monitor. In the event of an urgent unrelated toxicity, study treatment should be interrupted as per [Table 2](#). Dose re-escalation is not permitted.

Table 2: Dose Modifications for Tazemetostat Treatment-Related Toxicities (Cycle 2+)

Toxicity	During Therapy	Approximate Dose Adjustment
Grade 1		
All occurrences	Continue tazemetostat	Maintain dose level
Grade 2^{c, d}		
1st occurrence	Interrupt tazemetostat until resolved to Grade \leq 1 or baseline ^b	Maintain dose level
2nd occurrence (same or new toxicity)		Restart at 600 mg twice daily
3rd occurrence (same or new toxicity)		Restart at 400 mg twice daily
4th occurrence (same or new toxicity)		Discuss with Medical Monitor
Grade 3^c (Not Including Neutropenia and Thrombocytopenia)		
1st occurrence	Interrupt tazemetostat until resolved to Grade \leq 1 or baseline ^b	Restart at 600 mg twice daily
2nd occurrence (same or new toxicity)		Restart at 400 mg twice daily
3rd occurrence (same or new toxicity)	Discontinue tazemetostat	Not applicable
Grade 3 Neutropenia (ANC: $<1.0 - 0.5 \times 10^9/L$)		
ANC $< 1.0 \times 10^9/L$ 1st occurrence	Interrupt tazemetostat until resolved to ANC $\geq 1.0 \times 10^9/L$ ^b	Maintain dose level
2nd occurrence		Restart at 600 mg twice daily
3rd occurrence		Restart at 400 mg twice daily
4th occurrence	Discontinue tazemetostat	Not applicable
Grade 3 Thrombocytopenia		
1st occurrence	Interrupt tazemetostat until resolved to Grade \leq 1 or baseline ^b	Restart at 600 mg twice daily
2nd occurrence		Restart at 400 mg twice daily
3rd occurrence	Discontinue tazemetostat	Not applicable
Grade 4		
1st occurrence	Interrupt tazemetostat until resolved to Grade \leq 1 or baseline ^b	Restart at 600 mg twice daily
2nd occurrence (same or new toxicity)	Discontinue tazemetostat	Not applicable

Abbreviations: ANC = absolute neutrophil count

^a Excluding alopecia and nausea, vomiting or diarrhea not receiving adequate treatment.

^b An interruption of tazemetostat for more than 14 days due to any toxicity must be discussed with the Medical Monitor before treatment can be resumed

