10. MAJOR PROTOCOL DEVIATIONS

All protocol deviations will be listed for the safety population. Protocol deviations will be summarized by major and minor category and by study part. Predefined categories of major protocol deviations will include:

- Violation of inclusion/exclusion criteria

-
- Prohibited medications
 - Study drug compliance

Additional categories may be added during the course of the study but will be determined prior to database lock.

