14.1. STUDY DRUG EXPOSURE

The following summaries of study drug exposure will be presented:

Study Parts 1 and 2:

- Duration of tazemetostat exposure (weeks)

Duration of exposure (weeks) = [(date of last actual dose of tazemetostat – date of first dose of tazemetostat) + 1]/7.

Except for the first and last dose dates, this calculation is not adjusted for periods where dosing is interrupted or dose is recorded as 0.

- Duration of Exposure Category

Part 1	Part 2

 - Days 1-39 (Weeks 1-5.6) - Days 40-67 (Weeks 5.7-9.6) - Days 68-95 (Weeks 9.7-13.6) - Days 96-123 (Weeks 13.7-17.6) - Days 124-151 (Weeks 17.7-21.6) - 	
 - Days 1-26 (Weeks 1-3.7) - Days 27-54 (Weeks 3.8-7.7) - Days 55-82 (Weeks 7.8-11.7) - Days 83-110 (Weeks 11.8-15.7) - Days 111-138 (Weeks 15.8-19.7) -

- Total number of cycles of study drug tazemetostat administered, categorized as follows.
 - 1) **Part 1:** Cycle 1 starts on day 1 and finishes on day 39, and Cycle 2 will begin on day 40 (Cycle 2 day 1) and each subsequent cycle from Cycle 2+ onwards will be of 28-day duration.
 - 2) **Part 2:** Cycle 1 starts on day 1 and finishes on day 26, and Cycle 2 will begin on day 27 (Cycle 2 day 1) and each subsequent cycle from Cycle 2+ onwards will be of 28-day duration.

Part 1	Part 2

 - Cycle 1 (Days 1-39; Weeks 1-5.6) - Cycle 2 (Days 40-67; Weeks 5.7-9.6) - Cycle 3 (Days 68-95; Weeks 9.7-13.6) - Cycle 4 (Days 96-123; Weeks 13.7-17.6) - Cycle 5 (Days 124-111; Weeks 17.7-21.6) - 	
 - Cycle 1 (Days 1-26; Weeks 1-3.7) - Cycle 2 (Days 27-54; Weeks 3.8-7.7) - Cycle 3 (Days 55-82; Weeks 7.8-11.7) - Cycle 4 (Days 83-110; Weeks 11.8-15.7) - Cycle 5 (Days 111-138; Weeks 15.8-19.7) -

- Total amount of tazemetostat taken (mg) for Cycle 1 and all subsequent cycles, separately.
- Average dose intensity of tazemetostat:

Part 1:

- 1) For Cycle 1 (Days 1-39):
 - Average dose intensity (mg BID/day) = total amount of tazemetostat taken (mg) / (2*30) (days) (mg BID/day)
 - Planned average dose intensity (mg BID/day) = $[400*3+400*2*(12+15)]/(2*30) = 22,800/(2*30)=380$ (mg BID/day)
- 2) For Cycle 2 + onwards

Average dose intensity (mg BID/day) = total amount of tazemetostat taken (mg) / [2 * duration of exposure (days)] (mg BID/day)
 where duration of exposure (days) = [(date of last actual dose of tazemetostat – date of first dose of tazemetostat) + 1] (days)

Part 2:

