1) For Cycle 1 (Days 1-26):

- Average dose intensity (mg BID/day) = total amount of tazemetostat taken (mg) / (2* 22) (days) (mg BID/day)
- Planned average dose intensity (mg BID/day) = $[800*3+800*2*(12+7)]/(2*22) = 32,800/(2*22) = 745.45$ (mg BID/day)

2) For Cycle 2+ onwards

Average dose intensity (mg BID/day) = total amount of tazemetostat taken (mg) / [2 * duration of exposure (days)] (mg BID/day)
 where duration of exposure (days) = [(date of last actual dose of tazemetostat – date of first dose of tazemetostat) + 1] (days)

- For assessment of tolerability, numbers of subjects requiring dose reductions, treatment interruption or treatment discontinuation in response to AEs (based on action taken for reported AEs)

The following summaries of study drugs itraconazole in part 1 and rifampin in part 2 will be presented.

Study Part 1:

- Summary statistics for the total amount of itraconazole received (mg)
- Number (%) of subjects who received <4200 mg, 4200 mg and > 4200 mg of itraconazole

Study Part 2:

- Summary statistics for the total amount of rifampin received (mg)
- Number (%) of subjects who received < 5400 mg, 5400 mg and > 5400 mg of rifampin

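### Cycle 2+ compliance is measured against a fixed 800 mg twice daily, so protocol-directed reductions and holds lower the score of subjects who took every prescribed dose

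*SAP*

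**What the plan says.** SAP 14.2, the study drug compliance section, reports Cycle 1 and later cycles separately. For later cycles, in both parts, "Cycle 2+: Percentage of tazemetostat taken" is average dose intensity divided by 800 mg BID/day. It is summarised as a continuous variable and in four bands ("Category of percentage of tazemetostat taken"): at least 90%, 80 to under 90%, 70 to under 80%, and under 70%.

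SAP 14.1 gives the intensity as total mg taken over twice the duration, where duration runs from first dose date to last actual dose date. The same expression appears earlier in 14.1 for exposure in weeks, with the remark that, apart from the first and last dose dates, "this calculation is not adjusted for periods where dosing is interrupted or dose is recorded as 0".

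Protocol 7.5.1 confines dose modification to Cycle 2 and beyond. Table 2 (Protocol 7.5.2) directs holds ("Interrupt tazemetostat until resolved to Grade" 1 or below, or baseline) and lower dose levels ("Restart at 600 mg twice daily", "Restart at 400 mg twice daily"), and 7.5.2 rules out re-escalation. Protocol 9.2.4 also permits holds around palliative radiation and other symptom-control procedures, after discussion with the Medical Monitor.

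SAP 10 lists "Study drug compliance" among the predefined major-deviation categories, without a cut-off.

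**The concern.** Compliance should compare what a subject took with what the subject was told to take. From Cycle 2 on, the denominator is instead the full starting dose on every day between first and last dose, whatever was prescribed. That ratio is relative dose intensity, reported under a compliance heading.

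The SAP treats Cycle 1 differently. There the planned intensity counts only planned dosing days: 30 of 39 in Part 1 and 22 of 26 in Part 2. Planned non-dosing days are left out in Cycle 1, while directed hold days in later cycles count against the subject. Two different quantities share one label and one set of bands.

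What is at stake is interpretation. From the percentage alone, a reader cannot tell missed doses from doses the protocol withheld or reduced.

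**Working it through.** **The plan's own figures (SAP 14.1).** Both reproduce.
- Part 1, Cycle 1: [400×3 + 400×2×(12+15)] / (2×30) = 22,800 / 60 = 380 mg BID/day.
- Part 2, Cycle 1: [800×3 + 800×2×(12+7)] / (2×22) = 32,800 / 44 = 745.45 mg BID/day.

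The SAP gives no worked figure for Cycle 2+.

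**Formula for Cycle 2+ (SAP 14.1 and 14.2).** Score = 100 × {total mg / [2 × (last dose date − first dose date + 1)]} / 800. In the cases below every prescribed dose is taken, duration starts at the first Cycle 2+ dose, hold days fall inside the duration, and dosing resumes after each hold. Dose levels come from Table 2. The lengths of time are illustrative assumptions.

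- 800 mg for 28 days: 44,800 / 56 = 800; score 100%.
- 28 days at 800 mg, then 28 at 600 mg: (44,800 + 33,600) / 112 = 700; score 87.5%, band 80 to under 90%.
- 7-day hold in 56 days, otherwise 800 mg: (800×2×49) / 112 = 700; score 87.5%, same band.
- 14 days at 800 mg, 7-day hold, 35 days at 600 mg: (22,400 + 42,000) / 112 = 575; score 71.9%, band 70 to under 80%.
- 7-day hold in 84 days: 77/84 = 91.7%, top band.
- 14-day hold in 224 days: 210/224 = 93.8%, top band.
- Limit, 600 mg throughout: 600/800 = 75%.
- Limit, 400 mg throughout: 400/800 = 50%.

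**When the score leaves the top band.** Take one kind of change at a time, with the rest of the period at 800 mg.
- Share s of the time at 600 mg: 1 − 0.25s < 0.90 when s > 40%.
- Share s at 400 mg: 1 − 0.50s < 0.90 when s > 20%.
- Share h on hold: 1 − h < 0.90 when h > 10%.

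A hold after which dosing never resumes has no effect, because duration stops at the last actual dose.

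**With mg prescribed as denominator.** Every case above scores 100%, because mg taken equals mg prescribed.

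**A related ambiguity.** The Cycle 2+ formula does not say that the first dose means the first Cycle 2+ dose. Read literally from Day 1, with only Cycle 2+ mg in the numerator, a fully adherent subject with one 28-day Cycle 2 would score 28/(39+28) = 41.8% in Part 1 or 28/(26+28) = 51.9% in Part 2. That is probably not intended, but the text should say so.

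**The case against.** The arithmetic is hard to dispute. The case against concerns its reach.

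- **No one is labelled non-compliant.** A reader might infer that adherent subjects are scored as non-compliant, or counted as major deviations under SAP 10. The documents do not support either. SAP 14.2 has four unlabelled bands and no threshold. SAP 10 gives no cut-off and does not refer to 14.2, and a Table 2 reduction follows the protocol. This objection stands.
- **75% and 50% are not typical scores.** Cycle 2+ dosing starts at 800 mg twice daily and reductions come later. If later cycles are pooled, a subject who starts at 800 mg and is later reduced, with no hold or missed dose, stays above these limits. They would be reached only if single cycles were scored and one was spent wholly at the lower dose. This also stands.
- **Few subjects are likely to be affected.** Protocol 5.5.1 gives the most common adverse events leading to interruption in adults as 2% to 5% each, and those leading to reduction as under 1%. The study plans 24 completers. This stands with a caution: these are rates per event term, so totals may be higher.
- **Tolerability is reported elsewhere.** SAP 14.1 counts subjects with reductions, interruptions or discontinuations due to adverse events, and SAP 16.1 adds tables and a listing. These show who had an event-driven change. They do not correct the percentage, and they do not cover the holds permitted by Protocol 9.2.4 for other reasons. This answers the concern only in part.

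**Conclusion.** The Cycle 2+ compliance percentage is wrong as defined for any subject who takes every prescribed dose but has a Table 2 reduction, or a hold followed by resumed dosing. The score then lies below 100%, and the subject may fall into a lower band. One cycle at 800 mg followed by one at 600 mg, or a 7-day hold in 56 days, gives 87.5%; short holds or late reductions in a long exposure can stay at or above 90%. The sizes rest on the assumed durations and on counting from the first Cycle 2+ dose.

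The consequence is modest. It is confined to a descriptive table and probably touches few subjects. It does not reach the Cycle 1 PK comparison, since Protocol 7.5.1 allows no reductions or holds in Cycle 1 and replaces subjects who need them. The correction is still worth making, because the percentage does not measure what its heading says and no other output repairs it.

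**What to change.** In SAP 14.2, define Cycle 2+ compliance in both parts as 100 × mg taken / mg prescribed, summed by day from the first Cycle 2+ dose to the last actual dose. Mg prescribed should use the dose level in force on each day, and zero on hold days that Table 2 directs or Protocol 9.2.4 permits, identified from the recorded reason for each change. Adverse-event action-taken data alone would miss the 9.2.4 holds.

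Keep the present ratio to 800 mg BID/day as a separate line labelled relative dose intensity. In SAP 14.1, state that the first dose in the Cycle 2+ formula is the first Cycle 2+ dose.

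The cost is SAP wording and one extra derived variable. It depends on the prescribed dose and the reason for each hold being recorded in the dosing data, which the documents reviewed do not show and which should be checked against the eCRF. No dosing rule changes.

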15. EFFICACY ANALYSIS

No efficacy analysis will be performed. Listing for efficacy responses such as CR/PR/PD and overall survival will be provided if data are collected.

16. SAFETY OUTCOMES AND ANALYSIS

All safety summaries will be based on the Safety population.

16.1. ADVERSE EVENTS

AEs will be coded using MedDRA v23.1. Summary tables will be based on treatment emergent adverse events (TEAEs) which are defined as AEs that started or worsened in severity on or after the day of the first dose of study drug through 30 days after the end of study drug or the initiation of subsequent anticancer therapy, whichever is earlier. All AEs, treatment emergent or otherwise, will be presented in AE listings.

Each summary table will include the incidence (number and percentage) of subjects reporting any TEAE, as well as, by SOC and PT. A subject will be counted only once with an SOC, even if the subject experienced more than one TEAEs within that specific SOC (likewise for PT).

Investigator assessed severity grade will be based on the National Cancer Institute CTCAE v5.0. A subject will be counted only once with the worst severity grade within a SOC and/or PT.

Investigator assessed causality to study drug will be categorized as “not related,” “unlikely related,” “possibly related,” or “probably related” to study drug. For summary purposes, treatment-related TEAEs will include events with relationship to study drug classified as “not related” including both “not related” and “unlikely related” or “related” involving both “possibly related” and “probably related”. A TEAE with a missing causality will be classified as “related” to study drug. A subject will be counted only once at the strongest causality within a SOC and/or PT (related over not related).

TEAEs of special interest are defined in Section 12.4.2 of the protocol.

In accordance with the TEAE table presentation described above, AEs will be summarized as follows:

- TEAEs
- TEAEs of grade 3 or 4
- Treatment-related TEAEs
- Treatment-related TEAEs of grade 3 or 4
- TEAEs leading to dose interruption
- TEAEs leading to dose reduction
- TEAEs leading to discontinuation of study drug
- Serious adverse events (SAEs)
- Treatment-related SAEs

-
- TEAEs leading to death
 - TEAEs of special interest

For treatment-related summaries, relationship will be summarized by each study drug (Part 1: tazemetostat or itraconazole; Part 2: tazemetostat or rifampin).

Separate listings of SAEs, TEAEs leading to discontinuation of study drug, TEAEs leading to dose modifications, and TEAEs with an outcome of death will be provided. A listing of TEAEs of special interest will also be provided.

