5.5. Benefit:Risk Assessment

5.5.1. Clinical and Nonclinical Safety Profile

Based on nonclinical toxicology studies and the clinical experience as of 12 April 2021, this section summarizes the anticipated safety profile for tazemetostat.

Among the 895 adult and pediatric subjects treated with tazemetostat monotherapy, 857 (96%) subjects experienced at least 1 treatment-emergent adverse event (TEAE), with 597 (70%) subjects experienced TEAEs assessed as related to the study drug by the Investigator. Of subjects with TEAEs, 469 (55%) subjects had TEAEs of Grade 3 or 4 severity. Treatment-related grade 3 or 4 TEAEs occurred in 161 (34%) of subjects with grade 3 or 4 TEAEs.

The following treatment-emergent AEs, regardless of causality, have been observed in $\geq 10\%$ of adult subjects across clinical studies: nausea, fatigue, vomiting, diarrhea, anemia, decreased appetite, asthenia, dyspnea, constipation, thrombocytopenia, and abdominal pain.

The most common treatment-related treatment-emergent AEs in the adult subjects across clinical studies include: nausea, fatigue, asthenia, anemia, diarrhea, vomiting, thrombocytopenia, decreased appetite, neutropenia, and alopecia.

Of the 779 adult subjects receiving tazemetostat monotherapy, 326 (42%) experienced at least one treatment-emergent serious adverse event (TESAE). Treatment-related SAEs were reported in 58 (7%) of subjects. Of the 109 pediatric subjects, 52 (48%) experienced a TESAE, and 10 pediatric subjects (9%) experienced a TESAE that was assessed as related by the Investigator.

Of the 895 adult and pediatric subjects, 144 (16%) subjects died within 30 days of last dose of tazemetostat. Of the 144 deaths, 135 (94%) of the deaths were due to disease progression. In addition, 2 deaths, one that was due to intestinal obstruction and one with an unknown cause, were assessed as possibly treatment related by the Investigator.

Of the 109 pediatric subjects, 30 (28%) died on study within 30 days of last dose and 28 (93%) of those deaths were due to disease progression.

The most common TEAEs leading to tazemetostat dose interruption in the adult population were thrombocytopenia (5%), neutropenia (3%), and anemia and diarrhea (each 2%). The most common TEAEs leading to tazemetostat dose reduction across all populations were thrombocytopenia, neutropenia and diarrhea reported in $<1\%$ of adult subjects.

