12.5. Relationship to Study Drug

A qualified Investigator must make the determination of relationship to study drug for each AE. The Investigator should decide whether, in his or her medical judgment there is a reasonable possibility that the event may have been caused by tazemetostat.

The following should be considered when assessing the relationship of an AE to study treatment:

- Temporal relationship of the onset of the event to the first dose of study drug
- The course of the event, considering especially the effect of discontinuation of study treatment or the reintroduction of study treatment, as applicable
- Whether the event is known to be associated with the study treatment or with other similar treatments
- The presence of risk factors in the study subject known to increase the occurrence of the event
- The presence of non-study treatment-related factors that are known to be associated with the occurrence of the event.

Investigators must also systematically assess the causal relationship of AEs to the study drug using the following definitions (the decisive factor being the temporal relationship between the AE and administration of the study drug):

- **Probable:** A causal relationship is clinically/biologically highly plausible, there is a plausible time sequence between onset of the AE and administration of the study drug, and there is a reasonable response on withdrawal.
- **Possible:** A causal relationship is clinically/biologically plausible and there is a plausible time sequence between onset of the AE and administration of the study drug.
- **Unlikely:** A causal relationship is improbable, and another documented cause of the AE is most plausible.
- **Unrelated:** A causal relationship can be definitively excluded, and another documented cause of the AE is most plausible.

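### The SAP 16.1 sentence defining treatment-related TEAEs names every causality category: a drafting error that also leaves the table design open

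*SAP*

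**What the plan says.** SAP 16.1 first sets a four-level scale: "Investigator assessed causality to study drug will be categorized as “not related,” “unlikely related,” “possibly related,” or “probably related” to study drug". The next sentence is meant to turn that scale into an analysis grouping. It says that "treatment-related TEAEs will include events with relationship to study drug classified as “not related” including both “not related” and “unlikely related", and continues "or “related” involving both “possibly related” and “probably related". Two rules follow. On missing values: "A TEAE with a missing causality will be classified as “related” to study drug". On counting: "A subject will be counted only once at the strongest causality within a SOC and/or PT (related over not related".

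The same section then lists the AE summaries. Three depend on the definition: treatment-related TEAEs, treatment-related TEAEs of grade 3 or 4, and treatment-related SAEs. Each appears beside an all-causality counterpart. The treatment-related summaries are to be produced for each study drug within each part.

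The scale comes from Protocol 12.5. Of an unlikely relationship it says "A causal relationship is improbable, and another documented cause of the AE is most plausible"; of an unrelated event, "A causal relationship can be definitively excluded, and another documented cause of the AE is most plausible". Protocol 13.3 plans to present adverse events by relationship among other factors, and leaves the complete details of the safety analysis to the SAP.

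**The concern.** The sentence makes both the not-related group and the related group members of the treatment-related set. Under the Protocol's own definitions, the not-related group holds the events for which some other documented cause is the most plausible one. A definition that admits them no longer separates anything.

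Safety is a secondary objective in both parts. The trial has no concurrent control and enrols patients with advanced malignancy, who will have many events from their disease. Investigator causality is therefore the planned way of separating possible drug effects from background illness. If the rule were programmed literally, three named summaries would add nothing to the all-causality ones. If it is programmed by inference, two competent programmers could produce different tables under the same title.

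**Working it through.** No figure in the plan depends on this sentence, so there is nothing to reproduce. The check compares sets, followed by an illustration of size.

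**Step 1: what the sentence selects.**

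| Causality recorded | Group under SAP 16.1 | In the treatment-related set as written? | In it if limited to the related group? |
|---|---|---|---|
| Not related | not related | yes | no |
| Unlikely related | not related | yes | no |
| Possibly related | related | yes | yes |
| Probably related | related | yes | yes |
| Missing | related | yes | yes |

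As written, the set holds 4 of 4 categories plus missing, which is every TEAE. Limited to the related group, it holds 2 of 4 plus missing. The SAE pair would coincide only among treatment-emergent events, because the SAP's list names SAEs without that restriction.

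**Step 2: does another passage correct it?** SAP 7 refers to Section 16.1 for the handling of missing relationship. SAP 3.2, on changes from the protocol, does not mention causality grouping. No other SAP section defines treatment-related.

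**Step 3: what was intended?** Three features of SAP 16.1 make sense only with two disjoint groups: assigning missing causality to the related group, ranking related above not related, and listing all-causality and treatment-related summaries separately. Protocol 12.7 also takes possibly or probably related as the related group when it sets out which SAEs found after the study are to be reported.

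**Step 4: what remains open?**
- *Restriction.* The table keeps only related events. The table titles point this way.
- *Display of both groups.* The table shows related and not related events, each labelled. The by-relationship presentation in Protocol 13.3 points this way, and so does the ranking rule, which has work to do only where both groups are shown.

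The sentence does not choose between them.

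**Step 5: illustration of size.** Protocol 5.5.1 gives counts for 895 adult and pediatric subjects on tazemetostat monotherapy: 857 with any TEAE; "597 (70%) subjects experienced TEAEs assessed as related to the study drug by the Investigator"; 469 with grade 3 or 4 TEAEs; 161 with treatment-related grade 3 or 4 TEAEs. The Protocol's percentages use changing denominators: 597/857 = 70%, 469/857 = 55%, 161/469 = 34%. Put on the common base of 895:

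| | All-causality (literal rule) | Related only | Ratio |
|---|---|---|---|
| Any TEAE | 857/895 = 95.8% | 597/895 = 66.7% | 857/597 = 1.44 |
| Grade 3 or 4 | 469/895 = 52.4% | 161/895 = 18.0% | 469/161 = 2.91 |

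**The case against.** The strongest reply is that nobody would apply the sentence literally. Read to its end, it sets up two labelled groups, and the missing-value and ranking rules beside it would be pointless if everything were already treatment-related. It can also be read as describing a table that shows both groups side by side; on that reading no unrelated event is counted as related and nothing is inflated. The affected tables are descriptive and secondary, and all AEs will appear in listings in any case.

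Most of this stands. A reader might infer that the sponsor chose to count unrelated events as treatment-related, or that duplicate tables are certain. The documents support neither, because the surrounding rules contradict the first and the side-by-side reading defeats the second. A reader might also take 95.8% against 66.7% as what this trial would report. That is not supported either: the counts come from a wider monotherapy programme that includes pediatric subjects, whereas this trial plans about 40 adults given tazemetostat alone and then with itraconazole or rifampin.

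What does not stand is the conclusion that no change is needed. The sentence is an operative analysis rule, it is wrong as worded, and its intent can be recovered only as far as the two groups. The table design cannot be. A validator checking a related-only table against the SAP would find that it departs from the written text.

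**Conclusion.** Wrong as written, minor in severity. The definition names the whole causality scale, so its literal result is every TEAE. The two-group split is clearly what was meant; whether the tables restrict to related events or display both groups is not stated. Three descriptive safety summaries in each part are affected, for each study drug. The primary PK analysis is not affected.

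The set comparison rests only on the SAP text. The ratios of 1.44 and 2.91 rest on the programme counts re-based to 895 and on the literal rule actually being programmed, so they are a hypothetical illustration and not an expected bias.

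**What to change.** Replace the defining sentence in SAP 16.1 with:

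> For summary purposes causality to each study drug is dichotomised: not related = not related or unlikely related; related = possibly related, probably related or missing. Treatment-related TEAEs and SAEs are only those in the related group; any by-relationship table that shows both groups is titled as such.

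This keeps the SAP's missing-causality rule, settles what the three treatment-related summaries contain, and leaves room for the by-relationship presentation in Protocol 13.3 under its own title. The ranking of related above not related can stay for tables that show both groups.

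The cost is one replaced SAP passage and a check of the table titles, with no change to data collection or design. SAP 1 requires the plan to be final before database lock, so the change belongs in that finalisation.
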